27.2 Visits

Screening (Visit 1) and randomisation/baseline (Visit 2) should always be performed as on-site visits. If a site is unable to perform these visits on-site, screening and randomisation of new participants at that site should be on hold until on-site visits are possible.

On-site visits can be converted to remote visits (video, phone or similar) or home or off-site visits.

27.3 Assessments

Assessments used for safety or the confirmatory endpoints (i.e., Height measurements, x-ray, IGF-I and PRO questionnaires) should be prioritised.

Height measurements are only to be performed during on-site visits.

Specifications regarding how to perform assessments using remote visits or as home visits will be provided by Novo Nordisk or the vendor engaged by Novo Nordisk, if relevant. Specifications will include training for staff performing remote assessments.

Local laboratories or diagnostic facilities can be used for blood sampling, x-ray and ECG at the investigator's discretion if on-site visits are not possible or in case of temporary lockdown of the central laboratory. Findings for these assessments should only be reported in the CRF if they meet the definition of an AE (refer to Section 12).

Home measurements of weight for dosing calculations cannot be performed if on-site visits are not possible and mitigation measures should be mutually agreed between Novo Nordisk and the investigator if two consecutive weight measures are missed.

If the assessments for safety and supportive endpoints cannot be performed as outlined above, they should be performed at the first possible timepoint following the originally scheduled visit in agreement with Novo Nordisk.

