- Subjects should be treated with NNC0195-0092, █ mg/kg/week until NNC0195-0092 is available for prescription in their country or until August 2024 at the latest.
- The assessments planned for the end of treatment visit defined in the flow chart for cohort I (extension until NNC0195-0092 is available for prescription, [Table 2-4](#)) should be performed at this visit.
- If X-ray and ECG were performed within 6 months prior to the end of treatment visit, these should not be performed at the end of treatment visit. The follow-up visit will take place 30 days after last treatment in the trial, as described in the flow chart ([Table 2-4](#)).

For subjects in cohorts II and III the following applies:

- Subjects should be treated with NNC0195-0092 until August 2024, at the latest.
- The end of treatment visit should be performed August 2024, at the latest.
- The assessments planned for the end of treatment visit defined in the flow chart for cohorts II and III ([Table 2-5](#)) should be performed at this visit.
- If X-ray and ECG were performed within 6 months prior to the end of treatment visit, these should not be performed at the end of treatment visit.
- The follow-up visit will take place 30 days after last treatment in the trial as described in the flow chart ([Table 2-5](#)).

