8.6.5 X-Ray for bone age assessment

X-Rays of left hand and wrist for bone age (BA) assessment according to the Greulich and Pyle atlas¹⁹ will be taken according to section [2](#). In cohort II bone age assessment should only be performed in children if it is standard practice at the site.

The X-Ray images will be sent to a central imaging laboratory for evaluation. An X-Ray taken within 13 weeks prior to screening can be used as screening data if the image is acquired according to the required standards and available to be sent to the central imaging laboratory.

In order to evaluate eligibility of cohort I and III, the result of the central review of the screening X-Ray image must be available in order to evaluate inclusion criterion [9](#) (cohort I) or inclusion criterion [21](#) (cohort III) (Section [6.2](#)).

FOR GERMANY ONLY: only x-rays taken as normal routine (with regards to dose, frequency and timing of x-rays) during diagnose and thereafter yearly during treatment will be used. No extra x-ray will be performed for the study. **END OF TEXT ONLY APPLICABLE FOR GERMANY.**

The overall process for image acquisition, transfer, central analysis, reporting of results and archiving is described in the Imaging manual prepared by the central imaging laboratory.

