12.1 Definitions

Adverse event

An adverse event (AE) is any untoward medical occurrence in a subject administered product, and which does not necessarily have a causal relationship with this treatment.

An AE can therefore be any unfavourable and unintended sign (including an abnormal laboratory finding), symptom or disease temporally associated with the use of a product, whether or not considered related to the product.

An AE includes:

- A clinically significant worsening of a concomitant illness.
- A clinical laboratory adverse event (CLAE): a clinical laboratory abnormality which is clinically significant, i.e. an abnormality that suggests a disease and/or organ toxicity and is of a severity that requires active management. Active management includes active treatment or further investigations, for example change of medicine dose or more frequent follow-up due to the abnormality.
- Abuse and misuse of trial product: Abuse is defined as persistent or sporadic, intentional excessive use of a medicinal product, which is accompanied by harmful physical or psychological effects (e.g. overdose with the intention to cause harm). Misuse is defined as: Situations where the medicinal product is intentionally and inappropriately used not in accordance with the protocol or the terms of the marketing authorisation.

The following should **not** be reported as AEs:

- Pre-existing conditions, including those found as a result of screening procedures (pre-existing conditions should be reported as medical history or concomitant illness).
- Pre-planned procedures unless the condition for which the procedure was planned has worsened from the first trial related activity after the subject has signed the informed consent.

The following three definitions are used when assessing an AE:

- **Severity**
 - **Mild** - no or transient symptoms, no interference with the subject's daily activities.
 - **Moderate** - marked symptoms, moderate interference with the subject's daily activities.
 - **Severe** - considerable interference with the subject's daily activities; unacceptable.
- **Causality**

Relationship between an AE and the relevant trial product(s):

- **Probable** - Good reason and sufficient documentation to assume a causal relationship.
- **Possible** - A causal relationship is conceivable and cannot be dismissed.
- **Unlikely** - The event is most likely related to aetiology other than the trial product.

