27.1 Definition and scope of section

A major emergency is defined as a situation that causes substantial restrictions to study site access for participants and/or sponsor representatives.

In case local restrictions due to a major emergency (e.g., health outbreak, hurricanes, floods) lead to lock-down of a site, the site must contact Novo Nordisk to allow for implementation of mitigations mentioned in this section based on mutual agreement.

According to local regulation, health authorities and independent ethics committees should be notified in case elements of the emergency section are activated.

This section indicates the minimum requirements for assessments that should be performed during a lock-down, but sites should always try to follow the assessments outlined in the original flow chart (Section 2) to the extent possible. Implementation of specific mitigations should be based on assessment of feasibility at the individual site.

Sites should comply with local regulations, requirements and/or guidelines if they are issued.

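### Section 27.3 bars non-AE findings of emergency local tests from the CRF, so local ECG and safety laboratory results have no stated route to the database, and it leaves open whether local X-rays are read centrally

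*Combined protocol and SAP*

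**What the plan says.** Section 27.3 opens with a priority list: "Assessments used for safety or the confirmatory endpoints (i.e., Height measurements, x-ray, IGF-I and PRO questionnaires) should be prioritised". It then gives a fallback: "Local laboratories or diagnostic facilities can be used for blood sampling, x-ray and ECG", at the investigator's discretion, where on-site visits cannot take place or the central laboratory is temporarily closed. The next sentence limits what is kept: "Findings for these assessments should only be reported in the CRF if they meet the definition of an AE". A catch-up clause ends the section: "If the assessments for safety and supportive endpoints cannot be performed as outlined above, they should be performed at the first possible timepoint" after the planned visit. Section 27.1 calls these minimum requirements and adds that "sites should always try to follow the assessments outlined in the original flow chart" as far as they can.

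The AE threshold for a laboratory result is in Section 12.1: "a clinical laboratory abnormality which is clinically significant, i.e. an abnormality that suggests a disease and/or organ toxicity", and it must also be severe enough to need active management.

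Three other provisions bear on the point:

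- Section 8.6.5 on bone age: "The X-Ray images will be sent to a central imaging laboratory for evaluation".
- Section 8.6.4 on ECG: the investigator classifies the recording into one of three categories. No central reader is described.
- Section 8.3.3 waives both tests at the final treatment visit (the quote breaks off just before that visit is named again): "If X-ray and ECG were performed within 6 months prior to the end of treatment visit, these should not be performed at the end of". This is listed for cohort I children who continue past week 364 and for cohorts II and III, and is repeated in footnotes to Tables 2-4 and 2-5.

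**The concern.** The section names these assessments as the ones to protect in a lock-down, and then discards most of their results when they are done by the fallback it permits. Section 17.4.3 plans by-visit summaries of bone age against chronological age and of change from baseline in safety laboratory values. Such summaries need every value, including the normal ones. Section 8.12 asks investigators to make every effort to collect the data, which is hard to square with an instruction not to record results already in hand.

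At stake are laboratory follow-up and end-of-treatment safety records in a long extension. Section 12.7.2 ends the data monitoring committee's work after the safety extension, so later oversight relies more on routine surveillance. A drift in local results that stays below the AE threshold would not be visible through the CRF.

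**Working it through.** The plan states no figure on this point, so there is none to reproduce. The check sets the provisions side by side.

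**1. Route to the database, by test**

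| Test | Usual route | Route if done locally under 27.3 | Result below AE threshold |
|---|---|---|---|
| ECG | Investigator classification (8.6.4) | CRF only if an AE | No stated route |
| Safety laboratory, analysed locally | Central laboratory, electronic transfer (8.7, 15) | CRF only if an AE | No stated route |
| Blood drawn locally, analysed centrally | Electronic transfer (15) | Not revoked | Still arrives |
| X-ray for bone age | Image to central reader (8.6.5) | Not stated | May or may not arrive |
| Height | On site | On site only (27.3) | Rule does not apply |

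One trigger for local testing is closure of the central laboratory. Local analysis is then the evident purpose, so the third row is no help in that case.

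**2. Catch-up clause.** It applies when an assessment cannot be performed in the ways the section describes. A local test is one of those ways. Once it is done, the clause does not call for a repeat.

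**3. Six-month waiver.** The condition is that the X-ray or ECG was performed, not that a result is held. In Table 2-4 an ECG is due at visit 36 (week 416 + 1 day), and visit 38 is no later than week 442. The longest interval is (442 − 416) × 7 − 1 = 181 days, about 6 months. A visit-36 ECG therefore normally cancels the one at visit 38. If it was done locally and was not an AE, no ECG result is recorded at either visit. For X-ray the same follows only if the image was not read centrally.

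**4. Bone-age series.** In the long-term extension, Section 17.4.3 lists weeks 208, 260 and 364. If a week-260 image were not read, the gap would be 364 − 208 = 156 weeks, instead of intervals of 52 and 104 weeks.

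**5. Illustration with assumed inputs.** The documents do not give the share *q* of assessments done locally or the chance *p* that a finding is an AE. Assume *q* = 5% to 25% and *p* = 1% to 10%, with the 56 expected cohort I completers (Section 6.1.1) at one visit and all local tests analysed locally.

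- Not recorded = 56 × *q* × (1 − *p*): from 56 × 0.05 × 0.90 = 2.5 to 56 × 0.25 × 0.99 = 13.9.
- Recorded as AEs = 56 × *q* × *p*: from 56 × 0.05 × 0.01 = 0.03 to 56 × 0.25 × 0.10 = 1.4.
- Share of local findings unrecorded = 1 − *p*: 90% to 99%.

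**6. Would the means be biased?** Only if AE-grade local values were pooled with on-site values. With AEs taken as the upper tail of a standard normal with mean *m*, the shift is *qpm* / ((1 − *q*) + *qp*). At *q* = 0.05, *p* = 0.01, *m* = 2.665 it is 0.001 SD. At *q* = 0.25, *p* = 0.10, *m* = 1.755 it is 0.0439 / 0.775 = 0.057 SD. Nothing in the plan says such pooling will occur.

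**The case against.** The strongest reply is that the rule is narrow and partly sensible. It applies only in an emergency, by agreement with the sponsor, and sites are told to keep to the flow chart where they can. Analyses are central by default, and Section 8.7.7 has the central laboratory supply the IGF-I reference ranges and calculate the SDS, so mixing in local assays would harm comparability. The affected summaries are descriptive, and ECG is not named among those in Section 17.4.3. Section 3.1.6 describes the 26-week main period as completed.

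Much of this stands. It justifies keeping local IGF-I out of the SDS summaries and limits how serious the point is. It does not justify leaving ECG classifications and safety laboratory results unrecorded.

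A reader might also infer more than the documents support:

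- **That bone age is lost.** Section 27.3 restricts findings reported in the CRF. It does not revoke central reading, and Section 8.6.5 already accepts suitable images taken up to 13 weeks before screening. The imaging manual may settle the matter but is not available here.
- **That the summaries are selected for abnormality.** AE-grade findings are reported on AE forms and counted in AE tables. The likelier effect on the value summaries is that local results are absent, whether normal or not.
- **That any cohort I child could finish without a final ECG or X-ray because of the waiver.** The Section 8.3.3 waiver is not listed for cohort I children ending at visit 32.
- **That near adult height cannot be determined.** Sections 6.5.1 and 17.4.3 give a chronological-age fallback when bone age is missing.

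**Conclusion.** The point holds in a limited form. Section 27.3 contradicts its own priority list. Taken literally, it leaves locally classified ECGs and locally analysed safety laboratory results below the AE threshold with no route into the database. For X-rays the defect is an unanswered question, with possible rather than certain loss of bone age. Combined with the waiver, cohort I children past week 364 and children in cohorts II and III can end treatment with no recorded ECG, and possibly no bone age, although one was taken.

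The consequence is avoidable missing data in descriptive safety and bone-age summaries. The height endpoint is untouched by this rule, and AE incidence, the primary endpoint of cohorts II and III, keeps its AE-grade findings. The documents do not say how many children are affected. The 2.5 to 13.9 unrecorded results per visit rest wholly on the assumed shares. The conclusion also assumes that no manual or later instruction supplies the missing route. The text should be amended because the loss is easily prevented, not because a main result is in danger.

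**What to change.** Amend Section 27.3 and the waiver text as follows.

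1. State that local X-ray images meeting the imaging standard are sent to the central imaging laboratory with the acquisition date, and that the central reading is used as that visit's bone age.
2. Enter local ECG classifications in the CRF, whether or not they are AEs. Do the same for local safety laboratory results, flagged as local with units and reference range. List those laboratory values separately, and keep local IGF-I out of the SDS summaries.
3. In Section 8.3.3 and the matching footnotes to Tables 2-4 and 2-5, apply the 6-month waiver only where the earlier X-ray or ECG result is held in the trial database.

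The cost is amendment wording, an eCRF flag, some data entry and a separate listing for local assays. Where items 1 and 2 capture the local result, the child needs no extra procedure. Item 3 would lead to a repeat only where the result could not be retrieved, and its X-ray part must be reconciled with the Germany-only text in Section 8.6.5, which rules out extra X-rays for the study.
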